PROTOCOL:

**Be-Active Study – Increasing Physical Activity for Cancer
Survivors**

NCT05376293

Protocol Date – 10/28/22

BACKGROUND

Rates of cancer survivorship are exponentially rising and there is a growing need to address the unique health challenges facing cancer survivors. Although cancer is the second leading cause of death in the United States, cancer death rates have decreased by 27% over the last decade¹. Currently, there are >16.9 million cancer survivors in the US (~5% of the population) and it is estimated that rates of cancer survivorship will increase by an additional 31% by 2030 due to earlier detection and improved treatments². Survivorship is also more complicated as the proportion of people with advanced cancers experiencing prolonged survival also increases due to the increased effectiveness of precision and immunotherapies. In advanced melanoma, for example, median overall survival among study volunteers receiving nivolumab plus ipilimumab extended beyond six years³. While these predictions are encouraging, cancer survivors, whether in remission or with extended disease stability, and of a variety of cancer types, face unique health challenges resulting from the disease which can persist well beyond the end of cancer treatment and reduce physical and mental health-related quality of life. For example, among cancer survivors, 32% report continued limitations in daily activities⁴, 25% report persistent fatigue for years post-treatment⁵, 18% report anxiety symptoms⁶, 12-14% have clinical depression⁷, and up to 80% report some level of fear of recurrence⁸.

Physical activity (PA) is a modifiable lifestyle behavior which can help ameliorate these adverse health effects and is positively associated with numerous physiological and psychological health benefits. Findings from the American College of Sports Medicine's International Multidisciplinary Roundtable indicate that there is strong evidence that regular PA can improve common cancer-related side effects, namely anxiety, depression, fatigue, health-related quality of life, physical functioning, and cardiorespiratory fitness⁹. Physical activity is also associated with lower risk of all-cause mortality, cancer recurrence, and the likelihood of other comorbid chronic diseases (e.g., type 2 diabetes and cardiovascular disease)¹⁰⁻¹².

Although PA is important for cancer survivorship, the majority of cancer survivors do not meet recommended PA guidelines. Currently, it is recommended that cancer survivors engage in ≥ 150 min/week of moderate-intensity PA⁹. However, it is estimated that up to 47% of cancer survivors fail to meet this guideline as assessed via self-report PA measures¹³⁻¹⁷. This percentage is likely even higher, given that prior studies in cancer and non-cancer populations have shown three- to six-fold reductions in PA estimates when assessed via accelerometers (a wearable device to objectively-assess PA), versus self-report PA¹⁸⁻²⁰.

Despite strong evidence that regular PA has numerous health benefits for cancer survivors, *how to* promote sustained changes in PA among inactive cancer survivors is not well understood²¹. This is largely because the majority of high-quality randomized trials examining the effect of exercise training on health parameters for those living with cancer or beyond have utilized intense exercise training regimens, where supervised exercise is performed several times per week for multiple weeks at a laboratory or research center. While these studies are important and a necessary first step towards understanding the role of exercise in cancer prevention and survivorship, these strict exercise training protocols are unrealistic to implement on a large scale and have limited dissemination potential; thus it is necessary that effective and translatable interventions for increasing PA among cancer survivors are developed and implemented. In addition, there is a lack of evidence to inform whether these benefits extend to those survivors on extended treatments.

Automated, Internet-based PA programs allow for wide-scale dissemination at a relatively low cost. Pew Research data show that >90% of Americans use the Internet²², making it an ideal medium for delivering behaviorally-based PA interventions, as it can reduce provider costs and reach larger numbers of individuals. Further, the cost of delivering an automated Internet program is low, and there is no added cost for enrolling additional participants, which is important from a translation perspective into healthcare settings.

Although eHealth interventions are widely used to promote PA and other lifestyle behaviors in 'non-clinical' settings or for patients with specific chronic diseases (e.g., CVD, diabetes), application of these technologies to promote PA in cancer survivors lags behind and is a relatively new concept²³. A recent systematic review²³ identified only five Internet interventions targeting increases in PA among cancer survivors. Of those, only three were randomized trials with a control group, four used a self-report measure of PA, and four were <12 weeks in duration. While overall, these studies showed preliminary support that web-based interventions can increase PA among cancer survivors, additional research is clearly needed.

The proposed study addresses significant limitations in this area of research and examines the feasibility, acceptability, and preliminary efficacy of a 12-week, fully-automated Internet program for increasing PA among cancer survivors, by including those off all cancer treatment and those stable on continuous anticancer therapy - thereby adding to the scant body of literature examining the effect of Internet interventions in this population. It further extends the PA and cancer literature by using rigorous methodology (accelerometers) for assessing changes in PA, not limiting the inclusion criteria to one particular cancer type

(e.g., breast cancer only), utilizing a randomized design which allows for comparison to a usual care control condition, testing an Internet program that is driven by behavioral theory, incorporating the most effective behavioral intervention components (see Innovation), and addressing the need for longer-term interventions (>6 weeks) which also assess the maintenance of PA post-treatment (i.e., 24-wk assessment). Findings from this study have potential to lead to a larger trial with clinical implications for increasing PA in cancer survivors.

STUDY AIMS

- **Primary aim 1:** Evaluate the feasibility, acceptability, and engagement with the EEP. Feasibility will be evaluated using a comprehensive approach which includes measures of screening (# screened/mo), recruitment (# enrolled/mo), randomization (% eligible who enroll), and retention (% completing study). Acceptability will be assessed by a program satisfaction questionnaire at each assessment time point. Intervention engagement will be measured by the number of website logins, video lessons viewed, homework assignments completed, frequency of exercise planning, number of exercise days, and total exercise minutes.
- **Primary aim 2:** Compare treatment groups on 12- and 24-week changes in PA (steps, MVPA, bouts MVPA). We will stratify patients whether or not they are on maintenance/continuous treatments or not.
- **Secondary aim:** Compare treatment groups on changes in sleep, weight, and other questionnaire measures (e.g., fatigue, distress, anxiety, depression, health-related quality of life, fear of recurrence) at 12 and 24 weeks.

RESEARCH PLAN

Study Overview and Randomization. 50 participants will be randomized in equal numbers (permuted block structure, matched by biological sex and cancer type) at baseline to receive the 12-week Energize! Exercise Program (EEP) or to a standard of care control condition (CON). Assessments of PA, fatigue, sleep, distress, anxiety, depression, weight, health-related quality of life, and fear of cancer recurrence will occur at baseline, 12 weeks (post-intervention), and 24 weeks (following 12-week no-contact follow-up period). Following the 24-week assessment, participants randomized to CON will have the opportunity to participate in the EEP, if they desire, and complete an additional assessment at 36 weeks (upon completion of the EEP). Participants randomized to EEP will be provided with CON newsletters following the 24-week assessment.

Recruitment & Enrollment. Participants will be primarily recruited via multiple avenues within the Lifespan Cancer Institute (LCI), the Miriam Primary Care Clinic, and the Oncology, Wellness, Lifestyle and Survivorship (OWLS) clinic. We will work with our LCI Patient Navigators and Advanced Care practitioners who work closely with oncology and radiation oncology and will help to identify patients who will be eligible. Clinical research assistants may also access healthcare records prior to patient visits to identify individuals who meet our inclusion criteria related to age, BMI, and duration of time following cancer treatment. If eligible based on that information, they may send them a message informing them about the study via the patient portal, the standard of care mechanism of contact, or ask patients about their physical activity levels at visits or via phone. Research assistants will either direct individuals to the online screener or help patients complete the online screener for the study. However, we may also work with other physician groups, post flyers, and advertise on various social media platforms (e.g., Facebook, Instagram, Twitter) to help spread the word about our research study. All interested individuals will complete an online screener to determine initial eligibility. If eligible, a research staff member will conduct a follow-up phone screen to confirm eligibility and schedule an orientation session where the study will be explained in detail and informed consent will be obtained. All participants will also be required to get physician clearance (see attached MD consent form) prior to randomization.

Participants. Individuals must have a confirmed cancer diagnosis and have either completed all cancer-directed treatment in the past 12 months or be on a maintenance/continuous treatment regimen. Individuals must also be 18-70 years of age, have a BMI between 18.5 and 45, have daily Internet access, free of any medical condition for which PA is contraindicated, and inactive, defined as engaging in <60 min/week of moderate-intensity PA over the past 3 months. Participants must also be English speaking, as the Internet program is currently in English. These broad inclusion criteria were selected to enhance generalizability of study findings and to provide us with preliminary data on the effectiveness of this program across cancer types.

Internet-based exercise program. Participants randomized to EEP will receive the 12-week Energize! Exercise Program. This theory-driven, behaviorally-based Internet program is designed to increase moderate-intensity exercise to a level consistent with national recommendations and can be accessed via the Internet on a computer, smartphone, or other mobile device. Prior to the start of the program, participants will attend a 30-minute webinar in which they will be taught how to navigate the study website and will be given the opportunity to ask questions. Upon starting the program, they will be given a weekly exercise goal that starts at 75 min/wk and progresses to 150 min/wk. Participants will be taught how to gauge exercise intensity and the type of PA that will count towards their PA goals (i.e., moderate-intensity aerobic PA such as brisk walking, cycling). Activities such as hatha yoga, strength training, and household (e.g., gardening or vacuuming) and occupational activities (e.g., waitressing or delivering packages), do not meet the specified criteria for 'purposeful aerobic exercise' and would not be counted. To promote a regular habit of exercise, participants will be encouraged to exercise 5 days/week.

Participants will also be instructed to watch a 10-15 minute video weekly (Table 1). To help participants apply the intervention content, they will complete weekly homework assignments corresponding to each video lesson (~10 min to complete). Example assignments include creating exercise routines to promote habit formation, journaling about the value of exercise and positive feelings associated with exercise, evaluating their progress, and problem solving around exercise barriers. Participants will also plan their exercise prior to the start of each week and submit that detailed exercise plan via the study website. In addition to their planned exercise, they will report their actual exercise performed (e.g., minutes/day, time of day, and type of activity). Computer-generated personalized feedback will be provided weekly based upon the data that was input from the previous week. Feedback messages are designed to be encouraging and motivational, praising individuals for meeting goals. When goals are not met, support and encouragement are provided along with specific recommendations for behavioral strategies to implement. If participants do not report their exercise on the study website in a given week, an automated email will be sent, reminding them to do so.

Table 1: Video lesson titles

Week	Lesson title
1	Your exercise prescription
2	Exercise planning
3	Negative thoughts
4	Modifying your environment
5	Overcoming exercise barriers
6	Exercise enjoyment
7	Checking in with yourself
8	Managing exercise slips
9	Exercise motivation
10	Sitting less & moving more
11	Future-oriented mindsets
12	Thinking like a lifelong exerciser

Usual care control condition. Participants randomized to the usual care control condition will receive a newsletter, twice per month for the first 3 months, to help optimize retention rates. Consistent with information available to individuals via the National Cancer Institute and traditional survivorship care plans, these newsletters will focus on the health benefits of regular PA for cancer survivors, national PA guidelines, general information for initiating a PA program, exercise safety, gauging exercise intensity, and different types of exercise. Strategies for facilitating behavior change will not be included in these newsletters.

Feasibility, acceptability, and intervention engagement. Feasibility will be evaluated using a comprehensive approach which includes measures of screening (# completing online and phone screens/mo), recruitment (# enrolled/mo), randomization (% eligible who enroll), retention (% completing study), and treatment adherence (adherence to intervention)²⁴. These data will be used to develop and refine recruitment and assessment procedures, modify and improve intervention components, and inform sample size estimates for a larger efficacy trial. Acceptability will be assessed by a program satisfaction questionnaire. Participants will provide feedback on their overall satisfaction with the program, the program structure (e.g., planning, homework and feedback messages), and intervention content (e.g., video lessons). Further each week, as part of their homework, participants will be asked 3 brief questions about whether the information provided within the video lesson was helpful, informative, and whether it motivated them to exercise. There will also be an open-ended question to provide additional feedback. Intervention engagement will be generated automatically from the study website and measured by the number of website logins, video lessons viewed, homework assignments completed, frequency of exercise planning, number of exercise days, and total exercise minutes.

Assessment measures. Assessment will be completed at baseline, 12 weeks and 24 weeks (36-week assessment will also be conducted for CON participants who opt to enroll in the EEP following completion of their 24-week assessment visit). Participants will be compensated \$25 for completing weight, physical activity, and questionnaire measures (described below) at 12 weeks and also at 24 weeks (36 weeks if applicable), but not baseline. Participants will primarily be compensated with cash, but should the option of gift card or check will also be available for special circumstances (i.e., the participant is unable to come to an in-person visit).

Physical Activity. Physical activity will be objectively-assessed using the previously validated Actigraph accelerometer²⁵⁻²⁷. Participants will wear the accelerometer on their waist for 1 week, at each assessment, during all waking hours. Weekly MVPA (PA above validated count cut-point for moderate-intensity)²⁶, bouts MVPA (moderate-intensity PA occurring in bouts ≥ 10 min; measure of purposeful/ structured exercise), and daily steps will be computed. Intervention groups will be compared on these PA measures at 12 and 24 weeks. Self-reported physical activity will also be assessed using the Paffenbarger physical activity questionnaire.

Weight. Weight will be assessed at each assessment to the nearest 0.1 kg using standard procedures.

Questionnaire measures. Demographics, exercise history and exercise goals, and health literacy (*Single Item Literacy Screener*²⁸) will be assessed at baseline. A secondary aim of this trial is to examine intervention arms on measures of physical and mental well-being and PA constructs at 12 and 24 weeks. Health-related quality of life will be assessed using the *SF-36*. This previously validated and widely used questionnaire measure eight domains of health status: physical functioning, physical role limitations, bodily pain, general health perceptions, energy/vitality, social functioning, emotional role limitations, and mental health. Fatigue will be assessed using the *Brief Fatigue Inventory* which has been previously validated in a cancer population and is used to assess the severity of fatigue and the impact of fatigue on daily functioning. Individuals are queried about fatigue over the past week, current fatigue, and usual and worst fatigue in the past 24 hours. Sleep quality will be assessed using the *Pittsburgh Sleep Quality Index* which has been shown to have good reliability and validity. This 19-item self-rated questionnaire assesses sleep quality and disturbances over a 1-month time interval. Psychological distress will be assessed using the single-item *Distress Thermometer* developed by the National Comprehensive Cancer Network and asks patients to rate their distress on a scale of 0-10. Anxiety and depression will be assessed via the *Brief Symptom Inventory-18* which is a widely used to assess psychological symptoms of cancer survivors and has subscales related to somatization, depression, and anxiety. Fear of recurrence will be measured using the severity and trigger subscales of the *Fear of Recurrence Scale*²⁹. Physical activity constructs will include previously validated measures of exercise enjoyment (*Physical Activity Enjoyment Scale*), exercise self-efficacy (*Self-Efficacy for Exercise Scale*), exercise motivation (*Behavioral Regulation Exercise Questionnaire-2*), and exercise barriers (*Physical Activity Barriers After Cancer*). Program satisfaction will be assessed via a series of questions at 3 months.

REFERENCES

1. Centers for Disease Control and Prevention (CDC). An update on cancer deaths in the United States. US Department of Health and Human Services, Centers for Disease Control and Prevention, Division of Cancer Prevention and Control. <https://www.cdc.gov/cancer/dcpc/research/update-on-cancer-deaths/index.htm>

STATISICAL ANALYSIS PLAN:

Be-Active Study – Increasing Physical Activity for Cancer Survivors

NCT05376293

Analyses conducted 10/1/2024

The statistical analyses for this study were conducted using mixed-effects models to evaluate the impact of the program on various physical activity and psychological outcomes. The primary outcomes analyzed included self-reported moderate-to-vigorous physical activity (MVPA), total MVPA, and bouted MVPA over time.

For each outcome, mixed-effects models were employed, incorporating random intercepts for participants to account for the repeated measures design of the study. These models included fixed effects for time points, treatment arms, and their interaction, as well as baseline values of each outcome to control for initial differences across groups. Additional covariates such as age, BMI, weight, sex, education, racial/ethnic minority status, maintenance therapy, days since treatment completion, and daily wear time (for accelerometer-based outcomes) were also included. The primary interest was in the interaction between treatment arms and time points, which was used to evaluate whether changes in physical activity differed between the two groups (Energize! and Newsletter) at each time point (baseline, 3 months, and 6 months).

Post hoc pairwise comparisons of estimated marginal means (EMMs) were conducted to assess changes from baseline to 3 months and baseline to 6 months within each randomization group. Bonferroni corrections were applied to adjust for multiple comparisons.

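### The SAP's primary activity outcomes do not name steps and add self-reported MVPA, without reason, date or ranking, so an effect on self-report alone could be presented as primary

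*SAP*

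**What the plan says.** **Protocol.** Under Study Aims, primary aim 2 reads "Compare treatment groups on 12- and 24-week changes in PA (steps, MVPA, bouts MVPA". The Physical Activity paragraph under Assessment measures derives all three from a waist-worn Actigraph and then says "Intervention groups will be compared on these PA measures at 12 and 24 weeks". Only after that does it add: "Self-reported physical activity will also be assessed using the Paffenbarger physical activity questionnaire". No protocol aim names self-reported activity.

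**SAP.** The first paragraph says "The primary outcomes analyzed included self-reported moderate-to-vigorous physical activity (MVPA), total MVPA, and bouted MVPA over time". Steps appear nowhere in the SAP. The second paragraph lists daily wear time as a covariate for accelerometer outcomes, so total and bouted MVPA are presumably the device measures. The third paragraph mentions Bonferroni correction directly after describing post hoc within-arm comparisons, and does not say that it covers the three outcomes. The SAP is in the past tense, and its only date is that of the analyses, 10/1/2024. The protocol is dated 10/28/22.

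**The concern.** The primary list decides which results may be called primary. Here a named protocol outcome has lost any stated analysis, and a measure outside the protocol's primary list has taken a place. The documents do not show whether this happened before or after data were seen.

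The substitution also runs against the protocol's own argument. Its Background notes that of five earlier Internet trials "four used a self-report measure of PA", then says "The proposed study addresses significant limitations in this area of research" and offers accelerometry as the rigorous method.

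Participants cannot be blind to arm. Only in the Energize! arm is it the case that "they will be given a weekly exercise goal that starts at 75 min/wk and progresses to 150 min/wk". Those participants also log their exercise weekly, and "Feedback messages are designed to be encouraging and motivational, praising individuals for meeting goals". Reporting that differs by arm is therefore plausible for a questionnaire in a way it is not for a device. Its direction is not certain: the same participants are taught that some activities do not count, which could lower what they report, and controls also receive material on guidelines and intensity.

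**Working it through.** **1. The two lists**

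| Outcome | Source | Protocol primary aim 2 | SAP primary list |
|---|---|---|---|
| Daily steps | accelerometer | yes | not named |
| MVPA (SAP: total MVPA) | accelerometer | yes | yes |
| Bouts MVPA (SAP: bouted MVPA) | accelerometer | yes | yes |
| Self-reported MVPA | questionnaire | no | yes |

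Two of three are shared, one is unlisted and one is added. The finding rests on this comparison. The documents give no alpha, power or sample-size calculation, so there is no figure of the plan's own to reproduce. What follows is illustration.

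**2. How often chance alone gives a self-report-only primary result**

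Assumed inputs:
- six test statistics (3 outcomes × 2 follow-ups), jointly normal, with no true effect and no reporting bias;
- correlation 0.6 to 0.9 between the two device outcomes, 0.1 to 0.5 between self-report and device, and 0.5 to 0.7 between visits;
- full correlation matrix = outcome matrix ⊗ visit matrix;
- 1,000,000 draws for each of 18 combinations.

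The event of interest is self-report significant at either visit and neither device outcome significant at either visit.

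| Two-sided level per test | Any false-positive SAP primary | Self-report only |
|---|---|---|
| 0.05 | 17.5% to 23.2% | 5.5% to 7.9% |
| 0.025 | 9.5% to 12.5% | 3.2% to 4.3% |
| 0.05/6 = 0.0083 | 3.5% to 4.5% | 1.2% to 1.6% |

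At 0.05 per test, the self-report-only event makes up 28% to 39% of all trials with any false-positive primary. The SAP can also be read as one joint arm-by-time test per outcome. With a 2-df test at 0.05 per outcome, the self-report-only rate is about 3.6% to 4.7% and the any-primary rate 11.0% to 13.4%.

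**3. What differential reporting could add**

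The protocol plans 50 participants in equal numbers, so 25 per arm; assume no dropout. For a pure reporting shift of d standard deviations and no true effect, the standard error in SD units is √(2/25) = 0.283, and

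P(significant) = Φ(d/0.283 − 1.96) + Φ(−d/0.283 − 1.96).

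- d = 0: 5%
- d = 0.2: 11%
- d = 0.5: 42%
- d = 0.8: 81%

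These shifts are assumptions; the documents give none. The protocol's Background does cite device estimates three- to six-fold lower than self-report, but that concerns level, not a difference between arms.

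**4. What restoring the protocol list does not do**

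Three device outcomes at two visits, at 0.05 per test with the same device and visit correlations, still give some false positive in about 14% to 21% of trials. The change keeps every primary outcome device-measured and in the protocol. It does not by itself control multiplicity.

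**The case against.** The best case for the SAP has five parts.

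- **Wording.** The SAP says the primary outcomes included these three, so the list may not be complete and steps may have been analysed. That stands: the supportable statement is that steps are not named. But a protocol primary outcome still has no stated status, and self-report is still called primary.
- **No ranking in the protocol either.** True. But every activity measure named in aim 2 comes from the accelerometer, so its missing ranking gave no route to a self-report-only primary claim. The SAP opens that route.
- **The simulation does not measure the real worry.** Also true. Under the assumed null with no bias, self-report is just one more outcome weakly correlated with the rest. The rates show how often chance would produce the pattern; they do not size the reporting bias, and the joint-test reading lowers them.
- **Self-report was planned, and bias is not shown.** The questionnaire was in the protocol, and it is separate from the website log. No passage shows that one distorts the other. The issue is its promotion to primary, not its use.
- **This is a 50-person preliminary study.** Feasibility is aim 1 and the results are meant to inform a larger trial. Even so, the protocol labels the activity comparison a primary aim, and that later trial would build on whatever is reported as its result.

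**Conclusion.** The concern holds. The SAP's primary list is wrong as written: it does not name steps, it raises a self-report measure to primary, and it gives no reason, date or ranking. This follows from the text alone.

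The 5.5% to 7.9% self-report-only rate depends on the assumed 0.05 per test, two separate visits, the assumed correlations and no reporting bias. It falls to 1.2% to 1.6% at 0.05/6 and would rise with any reporting bias favouring the intervention. The documents do not show that the change was data-driven; they only leave that possibility open.

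**What to change.** 1. Fit the same mixed model to accelerometer daily steps, with wear time as a covariate, and report the result.
2. Treat steps, MVPA and bouts MVPA as the primary activity outcomes for aim 2, and report all three together. Any ranking among them chosen now would come after the analyses and should be labelled so.
3. Report self-reported MVPA as secondary, marked as not a protocol primary outcome.
4. Do not silently rewrite the list. Add a dated statement of how the SAP departs from the protocol, saying when and why the change was made and whether data had been seen.
5. Make no primary aim 2 claim on self-report alone. If self-report is positive and the device outcomes are not, present both side by side.

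The cost is one extra model on data the protocol already plans to compute, plus a short statement. The downside is that a self-report effect can no longer be called a primary finding. Disclosure at this stage informs the reader but cannot restore pre-specification.

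### Baseline is both a response and a covariate in the mixed model, so the stated control of initial differences does not reach the primary arm-by-time contrast

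*SAP*

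**What the plan says.** The second paragraph of the SAP describes a mixed model for each outcome, "incorporating random intercepts for participants to account for the repeated measures design of the study", with time, arm and their interaction as fixed effects.

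Baseline appears in that model in two roles:

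- **As a response.** The interaction is to show whether changes differ between the arms, which the SAP lists with the time points as "Energize! and Newsletter) at each time point (baseline, 3 months, and 6 months". The third paragraph then uses marginal means to "assess changes from baseline to 3 months and baseline to 6 months within each randomization group". A model-based change from baseline needs a baseline row in the response.
- **As a covariate.** The fixed effects are entered "as well as baseline values of each outcome to control for initial differences across groups".

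The SAP names the arm-by-time interaction as the primary interest. The other covariates include BMI and weight, and "daily wear time (for accelerometer-based outcomes) were also included". The SAP heading reads "Analyses conducted 10/1/2024", so these models have already been run.

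In the protocol, primary aim 2 is to "Compare treatment groups on 12- and 24-week changes in PA (steps, MVPA, bouts MVPA"). Under Study Overview and Randomization, "50 participants will be randomized in equal numbers (permuted block structure, matched by biological sex and cancer type"). Aim 2 also mentions stratifying by maintenance treatment. No allocation factor is baseline activity.

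**The concern.** A participant's baseline value is one number, added equally to the fitted value at all three visits. Such a term can shift a participant's overall level but not the change between visits, and the arm-by-time interaction is built from changes. The covariate therefore cannot do what the SAP says it does for the contrast the SAP cares about most.

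A reader would take the reported interaction as adjusted for chance differences in starting activity, when it is a change-score comparison. If the Energize! arm happened to start lower than the newsletter arm, regression to the mean would tend to inflate the apparent benefit; if it started higher, to shrink it. With two arms of 25 and no balancing on activity, such differences are to be expected, and the SAP tells the reader they have been dealt with.

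**Working it through.** **Inputs.** From the documents: 50 participants in equal arms, so 25 each; visits at baseline, 12 and 24 weeks; the model described above. The plan gives no SD, correlation, power or missing-data figure, so there is nothing of its own to reproduce. Assumed: correlation between baseline and follow-up, rho = 0.3, 0.5, 0.7; and k = baseline SD / follow-up SD = 1, 0.8, 0.7, with the follow-up SD set to 1.

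**Step 1: the covariate cancels.** Write the model for participant i at visit t as

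Y(i,t) = time(t) + arm + arm×time(t) + β·Y(i,0) + b(i) + e(i,t), t = 0, 1, 2.

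In Y(i,t) − Y(i,0), both β·Y(i,0) and b(i) drop out. With complete data the estimated interaction is the between-arm difference in mean change, whatever β is. The same holds for every other time-fixed covariate on the list. REML fits to simulated trials agree: the interaction with and without the baseline covariate differed by at most 9e-15 over 900 trials. In a separate set of fits, baseline plus eight time-fixed covariates changed it by at most 4e-15.

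**Step 2: what is left in the estimate.** The regression slope of follow-up on baseline is rho/k. So, per unit of chance baseline imbalance, the interaction moves by

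rho/k − 1.

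A one-SE imbalance is k·√(2/25). The interaction's SE is √[(2/25)(k² + 1 − 2·rho·k)]. The resulting shift, in units of that SE, is

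(k − rho)/√(k² + 1 − 2·rho·k).

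The large-sample variance of the change score relative to ANCOVA is (k² + 1 − 2·rho·k)/(1 − rho²), and its square root gives the ratio of interval widths.

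Example, rho = 0.5 and k = 1: slope 0.5 − 1 = −0.50; shift 0.5/√1 = 0.50 SE; variance ratio 1/0.75 = 1.33; interval ratio √1.33 = 1.15.

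Each cell below gives rho = 0.3 / 0.5 / 0.7.

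| k | Slope, formula | Slope, simulated, complete data | Slope, simulated, missing visits and varying covariates | Shift for one-SE imbalance (SE units) | Variance ratio | Interval wider by |
|---|---|---|---|---|---|---|
| 1 | −0.70 / −0.50 / −0.30 | −0.71 / −0.49 / −0.31 | −0.61 / −0.46 / −0.27 | 0.59 / 0.50 / 0.39 | 1.54 / 1.33 / 1.18 | 24 / 15 / 8% |
| 0.8 | −0.63 / −0.38 / −0.13 | −0.64 / −0.38 / −0.13 | −0.56 / −0.33 / −0.12 | 0.46 / 0.33 / 0.14 | 1.27 / 1.12 / 1.02 | 13 / 6 / 1% |
| 0.7 | −0.57 / −0.29 / 0.00 | −0.60 / −0.28 / 0.00 | −0.48 / −0.24 / −0.03 | 0.39 / 0.23 / 0.00 | 1.18 / 1.05 / 1.00 | 8 / 3 / 0% |

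The simulations used 3000 replicates per cell and no true effect. A model with only follow-up visits as responses and baseline as covariate had slopes of −0.03 to +0.02 with complete data.

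**Step 3: missing visits and visit-varying covariates.** The protocol measures weight at every assessment, and wear time can differ by visit, so exact cancellation need not hold in the real data. The fourth column assumes cumulative missingness of 10% then 20%, with wear time (0.3 SD per SD) and weight (−0.2 SD per SD) varying by visit. Here adding the baseline covariate moved the interaction by 0.12 to 0.19 SE on average. Removing it changed the slope on imbalance by at most 0.04. The covariate adds movement without adjustment.

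**Step 4: validity.** Null rejection of the SAP model was 3.9–5.2% with complete data and 5.0–6.1% with missing visits and varying covariates (t reference). A smaller run of 300 replicates gave 8.3% in one setting with missing visits and wear time; that is too few to rely on.

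**The case against.** The strongest reply is that nothing invalid results. The interaction is unbiased over randomization, its SE already covers chance imbalance, and its test holds close to its level. Primary aim 2 asks about changes, and the SAP itself presents the interaction as a comparison of changes. On this view, change score against ANCOVA is an efficiency preference in a 50-person feasibility trial. All of that stands and limits the point to the claim of control.

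The covariate is also not wholly inert. It partly adjusts the between-arm difference in marginal means at each visit: at k = 1 the 12-week difference had slopes on imbalance of −0.22 / −0.15 / −0.08, against −0.69 / −0.49 / −0.28 for the interaction in the same simulation. That is true, but the SAP's primary contrast is the interaction.

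The magnitude is assumed and can be nil. Entry requires less than 60 minutes of moderate activity a week, which makes a baseline SD below the follow-up SD plausible. At rho = 0.7 and k = 0.7 the effect is zero. At k = 0.5 the slope rho/k − 1 would be −0.40 / 0.00 / +0.40, so even its direction is uncertain. This stands. The entry rule narrows activity in both arms, however; it does not balance it between them.

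Finally, the double use of baseline is inferred from a short summary without model code. If baseline were not a response, the interaction would test only whether the arm effect differs between 3 and 6 months, and the stated changes from baseline could not come from the model's marginal means. The text needs correcting on either reading.

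**Conclusion.** The concern holds. As written, the primary contrast is a change-score comparison, and the stated control of initial differences does not apply to it. With complete data and time-fixed covariates this is exact and needs no assumed value. With missing visits or visit-varying covariates it rests on simulation under assumed settings, all of which gave the same answer.

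For 25 per arm and the assumed ranges of rho and k, an ordinary one-SE imbalance moves the interaction by between nothing and about 0.6 of its SE. The precision loss, from nothing to 24% in interval width, is secondary. This is not bias and not an invalid test. It is a property claimed for the primary analysis that the model does not deliver, and it should be corrected.

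**What to change.** **Preferred.** Model only the 12- and 24-week values as responses, with arm, visit, arm-by-visit, baseline and baseline-by-visit. Report the between-arm difference at each visit with a 95% confidence interval, which matches the comparison in the protocol's Physical Activity section. If wear time or weight enters visit by visit, include their baseline values too.

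**Alternative.** Keep baseline as a response, drop it as a covariate, constrain the arms to a common baseline mean, and use an unstructured covariance over the three visits with small-sample degrees of freedom. A random intercept alone is not enough if baseline and follow-up variances differ: at k = 0.7 it left slopes of +0.12 / +0.24 / +0.33 on imbalance and rejected a true null 7.7–8.2% of the time.

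**Minimum.** Keep the model, call the interaction a change-score comparison, and remove the control claim.

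**Cost.** One rerun on data already collected, or a wording change; no new patients or procedures. A rerun is post hoc given the analysis date, so it must be labelled so and shown beside the existing result. The preferred model gives up the within-arm changes from baseline as marginal-mean contrasts; the alternative, or the existing analysis alongside, retains them. A precision gain is not assured: at rho = 0.7 and k = 0.7 with missing visits and varying covariates, the existing model's variance was 0.89 of the preferred model's (0.96 once baseline wear time and weight are added) and 1.02 of the alternative's.
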